Sponsor/Sponsor- Investigator	Ente Ospedaliero Cantonale
Study Title:	The effect of informational videos on preoperative anxiety and satisfaction levels in patients undergoing elective ambulatory surgery. A prospective, randomized, controlled clinical trial.
Short Title/Study ID:	CERU-1801
Protocol Version and Date:	Version 1.1
Trial Registration:	www.clinicaltrials.gov NCT03581097
Study Category with Rationale	Provide the determined study category with explanation for this category
Background and Rationale:	
Anxiety is a common disorder in patients undergoing invasive procedures, reaching up to 60-80% in some series of these patients. Perioperative anxiety is associated with hemodynamic effects (like arterial hypertension and arrhythmias); it can have an impact on final surgical outcome, on anaesthetics drug dosage and also on rising of post-operative pain perception, leading to a substantial amount of analgesics prescription and post-operative hospitalization days. Finally, perioperative anxiety can reduce patient's overall satisfaction about quality of perioperative care.
 
Perioperative satisfaction is largely based on patients' expectations; it forms part of the surgeon's reward: satisfied patients are more likely to maintain good relationships with the surgeon, to abstain from the so-called "doctor shopping", to avoid malpractice proceedings and to recommend own surgeon to others. Last but not least, satisfied patients are more likely have better compliance about postoperative prescriptions and to attend follow-up appointments. In not life-threatening procedures however, main source of preoperative anxiety is often the anaesthesia outlook rather than surgery itself, largely related to a lack of information about anaesthetic procedure. These fears are largely underestimated in routine minor procedures (such as ambulatory surgery) and therefore real risk is not properly addressed. Due to lack of time and resources, this could have a significant impact on global patient satisfaction. Also if major complications are surgery-related (e.g. cardiac mortality), anxiety is also associated with poor surgical outcome. How to identify and treat patients who will likely benefit from more information about anaesthesia is an important question that remains relatively unaddressed. However, it's

	known that more information about surgery reduces the level of anxiety and apprehension.
Objective(s):	For these reasons we developed this study with a short educational video concerning global management of local anaesthesia on outpatient hand surgery. The aim of this trial was to assess the impact of this educational video about perioperative patients' anxiety levels.
Outcome (if applicable, see Basisformular): Primary Outcome Secondary Outcome	The principal outcome was to see and analyse the difference in preoperative anxiety between the two groups measured on our adapted visual analogue scale (VAS-A). Secondary outcomes were to perceive any disparity in patient's satisfaction degree measured through final questionnaire, and any variance in vital parameters that are usually affected by anxiety (like arterial blood pressure [mmHg], respiratory rate [breath per minute] and heart rate [beat per minute]) in all patients. A subgroup analysis was then performed, but applied to specific subgroups, like anxious patients, higher anxiety score (3 or more) and patients at their first experience with surgery.
Study Design, see Basisformular:	This is a prospective, randomized, controlled clinical trial.
Inclusion/Exclusion Criteria, see Basisformular:	Inclusion criteria were patients older than 18 years, ASA I-III patients undergoing elective hand-surgery operation and patients anesthetized by IVRA. Exclusion criteria were patient refusal, on-going anxiolytic or anti-depressive therapy, diagnosis of anxiety or psychiatric disorders, general contraindications to IVRA, limited compliance or language barriers.
Measurements and Procedures:	Patients were admitted on the same day of surgery in the day-hospital clinic, 2-3 hours before the operation; all vital parameters (non-invasive arterial blood pressure, respiratory and heart rate) were measured and they were asked to indicate their initial level of anxiety using some validated instrument, like the VAS-scale (discussed right below). Patients were randomized with a free web tool (available at www.randomizer.org) in a consecutive order into two parallel groups; last Author was the responsible of this randomisation and he was not directly involved in patient treatment. Surgeon and investigators involved in subsequent data analysis were blinded to group assignment.
Study Product/Intervention according to KlinV, if applicable:	One hour before surgery, patients assigned to the video-group (group I) visualised a Patient Education Video , a brief video (6 minutes). Patients in the film group watched the movie using a laptop computer equipped with headphones, and VAS score (Visual Analogue Scale) was repeated after the film. Video was recorded by the Anaesthesiology department team, in order to explain and show in a detailed way on a model, the sequence of events, which occurs between the arrival of patients in the operating room and the performance of intra-venous regional anaesthesia. The video began with an actress interpreting a patient scheduled for an elective outpatient hand surgery procedure acceding the day hospital clinic. It showed the interaction between the patient and the nurses who explain in details what is going to happen next and lead her through the preparation routine. The camera then followed the patient as she is accompanied to the induction room and the video showed all the details of the checks made as the patient accedes the operating room, the time-out and the preparation for the anaesthetic procedure, with the monitoring of the vital parameters. Then the intra-venous regional anaesthesia procedure was shown in details as an anaesthesiologist explains it step by step. The video concluded with the patient being brought to the operating room and staying awake and pain free as a simulated procedure begins.
Comparator(s) (if applicable):	Patients assigned to the control group (group II) did not see the video and underwent an otherwise identical preoperative preparation procedure.
Study Duration:	Around 8-9 months

Study Schedule:	From April to December 2013
Investigator(s):	
1. Dr. med. [name] Medico Aggiunto, Dip. Chirurgia della Mano ORBV, Bellinzona
 
2. Dr. med. [name] Medico Assistente, Serv. Anestesia ORBV, Bellinzona
 
3. Dr. med. [name] CapoClinica Medicina Intensiva, HUG, Geneva
 
4. Dr. med. [name] VicePrimario Chirurgia Toracica, ORBV Bellinzona
 
5. Dr. med. [name] VicePrimario Chirurgia Generale, ORBV Bellinzona
 
6. Dr. med. [name] VicePrimario Serv. Anestesia e Rianimazione ORBV, Bellinzona

Study Centre(s):	This is a single-centre study, to ORBV, Bellinzona
Statistical Analysis incl. Power Analysis	A power analysis was conducted before starting recruitment. According to Ayrat et al, as well according to estimated clinically relevance of diminution for anxiety, assuming a reduction of at least 50% in preoperative anxiety level as clinically significant, 45 patients per group were necessary (allowing for drop-outs) to reach a 95% level of significance with a power of 90%. We conducted a statistical frequency analysis regarding common vitals parameters and anxiety level according to VAS-scale at arrival in the hospital, before to go to the pre-operative room and at arrival at the pre-operative room, performing a statistical frequency analysis comparing all these three steps and all subgroup according to secondary outcomes.
GCP Statement:	This study will be conducted in compliance with the protocol, the current version of the Declaration of Helsinki, the ICH-GCP or ISO EN 14155 (as far as applicable) as well as all national legal and regulatory requirements.

Recruitment Procedure (if applicable: Advice/Flyer have to be submitted ; if applicable, please indicate the Localisation / Medium (which Newspaper))

All patients underwent two surgical pre-operative visits, during which they received detailed information about surgical procedure and provided their informed consent.

Study Procedure/Flowchart with Timelines: Study specific Examinations have to be clearly identified

Patients were randomized with a free web tool (available at www.randomizer.org) in a consecutive order into two parallels groups; last Author was the responsible of this randomisation and he was not directly involved in patient treatment. Surgeon and investigators involved in subsequent data analysis were blinded to group assignment. One hour before surgery, patients assigned to the video-group (group I) visualised a *Patient Education Video*, a brief video (6 minutes) better described below. Patients assigned to the control group (group II) did not see the video and underwent an otherwise identical preoperative preparation procedure. Patients assigned to the two different groups were kept always separated while waiting for surgery.

After the end of the video and at least 30 minutes before the transfer to the operating room (OR), investigators asked patient to indicate again its own anxiety level. Non-invasive arterial blood pressure, cardiac and respiratory frequency were recorded once again on arrival in the OR and monitored continuously throughout the anaesthetic and surgical procedure.

IVRA was performed by an anaesthesiologist and a nurse in the induction room outside the OR using a standardized procedure. Two intravenous lines were placed on each hand; after tourniquet inflation, a total volume of 40 ml of chloroprocaine 0.5% was injected intravenously in the operated limb. The patient was then transferred to the OR and 10 minutes after local anaesthetic injection, the surgeon tested loss of sensitivity with a pinprick test, after which surgery began.

As anxiety is a highly subjective psychiatric disorder, according to other investigational groups we felt that the best way to determine the state of anxiety is to let it evaluate directly by the patient. The VAS score (Visual Analogue Scale) is a valid instrument used for measuring anxiety. We chose an adapted VAS score (VAS-A), a semi-quantitative numerical scale (0 – 5 level) to measure patients' anxiety level, asking each patient to subjectively quantify its own anxiety, putting a mark on this visual scale, representing its actual anxiety degree.

At the end of the surgical procedure all patients were transferred directly to the day-hospital clinic. Between 1 - 3 hours after the operation all patients completed a satisfaction questionnaire with close evaluation from 0 to 10 regarding these topics: environment, equipment, organization, waiting time, pharmacy, nurses, professionalism, information, dedicated time. Moreover, video-group patients received a specific feedback questionnaire about the video, in which they were asked about personal satisfaction and video's education value (like informative and a valuable source of information for patients before local anaesthesia). Finally, we asked them if the educational movie made them more anxious or calmer.

Risks/ Inconveniences, which are Study specific:

No risk, because the intervention is a movie of 6 minutes.

Coverage of Damages: Insurance (yes/no)? Sum?

No

Storage of Data-and Samples for Future Research Aims: yes/no?,

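### The statistical section plans a three-step frequency analysis but no between-arm estimate of VAS-A adjusted for the admission score, and its steps do not line up with the measurement schedule

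*Combined protocol and SAP*

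**What the plan says.** The Outcome section sets the principal outcome as "the difference in preoperative anxiety between the two groups measured on our adapted visual analogue scale (VAS-A"). It adds a subgroup analysis "applied to specific subgroups, like anxious patients, higher anxiety score (3 or more) and patients at their first experience with surgery".

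The section Statistical Analysis incl. Power Analysis is the only statistical text. It treats a reduction of at least 50% in preoperative anxiety as clinically significant and gives 45 patients per group, drop-outs allowed for, with 90% power. Its method is a frequency analysis of vital signs and VAS at three steps: arrival in the hospital, before leaving for the pre-operative room, and arrival there. It ends "performing a statistical frequency analysis comparing all these three steps and all subgroup according to secondary outcomes".

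On timing, Measurements and Procedures says that at admission vital signs were taken and "they were asked to indicate their initial level of anxiety using some validated instrument, like the VAS-scale". For the video group, Study Product/Intervention says "VAS score (Visual Analogue Scale) was repeated after the film". Study Procedure/Flowchart with Timelines puts the second anxiety rating after the video and no later than 30 minutes before transfer. It puts the next vital signs on arrival in the OR, with monitoring through anaesthesia and surgery. Controls "did not see the video and underwent an otherwise identical preoperative preparation procedure". VAS-A is a semi-quantitative scale from 0 to 5.

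**The concern.** The outcome is a contrast between arms. The written analysis compares steps and subgroups. Comparing steps is a within-patient contrast and does not by itself deliver the principal outcome. The statistical section does not say which VAS-A reading is primary, what effect measure is reported, or with what interval. So no planned result can be set against the 50% reduction that the plan itself calls clinically significant.

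The admission VAS-A is taken before the video and is listed among the steps, yet it is not used as a baseline covariate in a comparison of arms. That gives up precision already paid for.

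The three steps also do not correspond to what the schedule says was measured and when. This leaves open which steps hold VAS-A data and what the second vital-sign reading represents.

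**Working it through.** **The plan's own figure.** The 45 per group can be neither reproduced nor refuted, because the plan gives no mean, SD, rate, test, sidedness or drop-out rate. Working backwards with the normal approximation, two-sided 5% and 90% power:

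- d = (1.960 + 1.282) / √(45/2) = 0.683. A halved mean then implies SD/mean = 0.5/0.683 = 0.73.
- On a proportion basis, 60% / 67% / 70% / 80% halved needs 56 / 45 / 41 / 30 per group.

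So 45 is attainable on either basis. The point does not depend on which was used.

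**Gain from adjusting for admission VAS-A.** The documents give no correlation ρ between admission and post-video scores, so a range is assumed. The residual SD is multiplied by √(1−ρ²), and power = Φ(d√(n/2)/√(1−ρ²) − 1.960). At n = 45, d√(n/2) = 3.242.

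| ρ (assumed) | √(1−ρ²) | CI narrower by | Power, 45 analysed |
|---|---|---|---|
| 0.3 | 0.954 | 5% | 92.5% |
| 0.5 | 0.866 | 13% | 96.3% |
| 0.7 | 0.714 | 29% | 99.5% |

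A simulation of scores rounded and clipped to 0-5 used 20,000 trials per scenario, an assumed control mean of 1.5 or 2.0 halved by the video, and an SD solved for 90% unadjusted power at 45. At ρ = 0.3 / 0.5 / 0.7 the CI width ratios were 0.96 / 0.88 / 0.74. Power was 92.0% / 95.8% / 99.3% for mean 1.5 and 91.9% / 95.5% / 99.2% for mean 2.0. ANCOVA type I error was 4.8-5.3%. At ρ = 0.1 power stayed at 90%, with no gain.

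**Drop-out allowance.** The table takes 90% power at 45 analysed, but the 45 already allows for drop-outs. If 90% is meant at, say, 40 analysed (an assumption), d = 3.242/√20 = 0.725. At 45 analysed, d√(n/2) = 0.725 × 4.743 = 3.439, and unadjusted power is Φ(3.439 − 1.960) = 93%. Adjusted power is then about 95% / 98% / over 99%, so the gain in percentage points is smaller. The narrowing of the CI is unchanged.

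**Why not a change score.** If the step comparison were turned into a between-arm comparison of changes, the SD would be multiplied by √(2(1−ρ)). At d = 0.683 and n = 45, power is 78% / 90% / 99% at ρ = 0.3 / 0.5 / 0.7. That is below the unadjusted 90% at the lowest correlation and never above ANCOVA.

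**Steps against schedule.**

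| Step in the statistical section | VAS-A in the schedule | Vital signs in the schedule |
|---|---|---|
| Arrival in hospital | yes | yes |
| Before leaving for the pre-operative room | after the video, before transfer | not described |
| Arrival at the pre-operative room | not described | on arrival in the OR (a different place name) |

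Three points exist in total, but each variable is described at only two of them; after arrival in the OR, vital signs are also monitored.

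**Vital signs and IVRA.** Study Procedure/Flowchart with Timelines records vital signs on arrival in the OR and monitors them through the anaesthetic, which suggests arrival comes first. Its next paragraph performs IVRA in the induction room outside the OR and transfers the patient afterwards. Both cannot describe the same arrival.

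**The case against.** The strongest reply is that the between-arm intention is already stated under Outcome, that randomisation makes an unadjusted comparison valid, and that ANCOVA is a preference whose benefit rests on assumed correlations. Most of that stands. Nothing here shows bias. On a proportion basis (67% halved, assumed) a 2x2 test at 45 per group has 89-90% power, so there is no shortfall against the plan. What the reply leaves unanswered is that the statistical section still gives no estimate, interval or primary time point.

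A reader might infer four stronger things that the documents do not support.

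- That the admission VAS-A goes unused. It is the first of the three steps; it is only not used as a covariate between arms.
- That the intervention description contradicts the schedule, because the video shows "the sequence of events, which occurs between the arrival of patients in the operating room and the performance of intra-venous regional anaesthesia". That passage describes the content of a film. It also shows the induction room first and ends with the patient being taken to the operating room, so it gives both orders.
- That controls have no second VAS-A. Their preparation is described as otherwise identical, and the instruction to ask again is not limited to the video group. What is missing is a time for controls that matches the video group's, since the end of a video gives them no anchor.
- That the vital signs are contaminated by IVRA. Monitoring through the anaesthetic, and the name pre-operative room, both favour an earlier reading. The order is unclear; contamination is not shown.

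**Conclusion.** The concern holds in limited form and should be fixed. The principal outcome is a between-arm difference, but the only statistical text plans a frequency comparison of steps and subgroups, without a between-arm estimate, CI or primary time point, and without admission VAS-A as a covariate. The cost of not adjusting is precision only: a CI wider than it need be, by an amount that depends on an undocumented correlation and vanishes near 0.1. The power figures further assume that the 90% refers to 45 analysed per group. It would be wrong to conclude that the trial is biased or underpowered for this reason.

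The step mismatch is real but moderate. The schedule supplies three time points in total; the plan does not say which variable belongs to which. The position of the second vital-sign reading relative to IVRA cannot be settled from the text. The precision argument also assumes that controls gave a second VAS-A at a comparable time.

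**What to change.** State the primary analysis as VAS-A at the post-video, pre-transfer assessment, compared between groups as randomised by ANCOVA with group and admission VAS-A as terms. Report the adjusted mean difference with its 95% CI. Report the same result as a percentage of the adjusted control mean, with its CI, so that it can be set against the 50% reduction; this reads the 50% as between arms, which the plan does not specify. Because the scale runs from 0 to 5, add a proportional-odds model with the same terms as the sensitivity analysis. This does change the status of the existing plan: step-to-step frequencies become descriptive and subgroup comparisons exploratory.

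Reconcile Outcome, Measurements and Procedures, the statistical section and Study Procedure/Flowchart with Timelines on three matters: which variable is measured at which step, when controls gave the second VAS-A, and whether arrival in the OR comes before or after IVRA. Only then analyse each vital sign between groups, adjusted for its admission value.

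The study is dated "From April to December 2013" and the analysis is described in the past tense. If the data have already been analysed, report this model beside the original analysis and label it post hoc. If controls turn out to have no comparable second VAS-A, say that the primary comparison cannot be made.

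The cost is wording and one re-run on data that the storage section says are archived, with no new patients or visits.

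### The subjective primary anxiety rating is requested by investigators after the film with no stated blinding of those who ask, so reporting bias could differ between arms

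*Combined protocol and SAP*

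**What the plan says.** The Outcome section makes the between-group difference in preoperative anxiety on the VAS-A the primary outcome, without naming a time point. The Study Procedure section describes the measure as a 0-5 scale, "asking each patient to subjectively quantify its own anxiety, putting a mark on this visual scale".

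On how the repeat rating is obtained, the same section says: "After the end of the video and at least 30 minutes before the transfer to the operating room (OR), investigators asked patient to indicate again" the anxiety level. The Study Product/Intervention section says of the film group that the "VAS score (Visual Analogue Scale) was repeated after the film". The Statistical Analysis section lists three VAS points: hospital arrival, before leaving for the pre-operative room, and on arrival there.

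The only blinding statement appears under Measurements and Procedures and again under Study Procedure: "Surgeon and investigators involved in subsequent data analysis were blinded to group assignment". On the film itself: "Video was recorded by the Anaesthesiology department team". Controls "did not see the video and underwent an otherwise identical preoperative preparation procedure", so there is no sham or attention film. The Study Procedure section adds that the two groups were kept apart while they waited.

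**The concern.** A patient who has just seen a film and is then asked by a member of the study team how anxious they feel may give a kinder answer than they otherwise would. An asker who knows the arm may also prompt, unintentionally, in the expected direction. Neither blinded party prevents this. The surgeon has no stated part in collecting the VAS-A, and blinding the analysts cannot remove bias already in the patient's mark.

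The stake is the primary comparison. A fall in score caused by courtesy or prompting looks the same in the data as a real fall in anxiety, and its most plausible direction favours the hypothesis.

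**Working it through.** **What the text establishes about collection**

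1. Who marks the scale: the patient. Who asks: investigators. Who is blinded: surgeon and analysts. For the people who ask, the plan is silent.
2. Link to the film: the anaesthesiology department made it. The Investigator(s) list has six entries, of which two (numbers 2 and 6) are from that service.
3. Timing: the film starts one hour before surgery and lasts 6 minutes, leaving 60 - 6 = 54 minutes. The rating comes at least 30 minutes before transfer, so it falls at most 54 - 30 = 24 minutes after the film, and less because transfer precedes surgery.

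**How much a reporting shift could matter**

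The plan has no figure for this bias. Its one relevant number, 45 per group, cannot be reproduced, because no mean, standard deviation, event rate, drop-out rate or sidedness is given. I take it as it stands.

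Inputs:
- n = 45 per arm (Statistical Analysis section);
- two-sided test at 0.05 (my reading of the stated 95% level; sidedness is not given);
- true effect zero;
- SD 1.0 to 1.5 points (assumption);
- mean reporting shift b in the video arm of 0.25 or 0.5 points (assumption). On whole levels this means a quarter or a half of video patients marking one level lower.

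Formula (normal approximation): SE = SD × √(2/n), and rejection probability = Φ(b/SE - 1.96) + Φ(-b/SE - 1.96).

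- SD 1.0: SE = √(2/45) = 0.211.
  - b = 0.25: b/SE = 1.186; Φ(-0.774) + Φ(-3.146) = 0.220.
  - b = 0.5: b/SE = 2.372; Φ(0.412) + a negligible term = 0.660.
- SD 1.5: SE = 1.5 × 0.211 = 0.316.
  - b = 0.25: b/SE = 0.791; Φ(-1.169) + Φ(-2.751) = 0.124.
  - b = 0.5: b/SE = 1.581; Φ(-0.379) + a negligible term = 0.353.

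The two-sample t-test gives nearly the same results:

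| SD (assumed) | shift 0.25 | shift 0.5 |
|---|---|---|
| 1.0 | 21.6% | 65.0% |
| 1.3 | 14.7% | 43.8% |
| 1.5 | 12.2% | 34.6% |

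The nominal rate is 5%. The plan names no test beyond a frequency analysis, and 45 already allows for drop-outs. With fewer analysed patients these rates would be somewhat lower.

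**The case against.** The strongest reply is that the plan does not say the collectors were unblinded; it says nothing about them. That is right, and it limits several stronger readings that a reader might infer:

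- *That the rating was taken face to face, without privacy, straight after the film.* The text says investigators asked and the patient made a mark. It does not describe the setting, and the interval could be up to about 24 minutes.
- *That the asker knew the arm.* Separate waiting makes this easy to infer, but no passage says who asked or what they could see. Nor does any passage say that the askers made the film.
- *That the bias can enter one arm only.* Courtesy towards the film can arise only in those who saw it. Interviewer expectation, or disappointment among controls who know of the film, could also move control ratings. Differential bias is the most that can be said.
- *That this is the only rating after the intervention.* The Statistical Analysis section also lists one on arrival in the pre-operative room. No blinded collector is stated for that one either.

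It is also fair to say that the shifts and SDs are assumed. The calculation shows what such a bias would do, not that it occurred. Blood pressure, heart rate and respiratory rate are secondary measures less open to courtesy, but they are non-specific and do not protect the primary outcome.

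Finally, the change may come too late. The Study Schedule gives April to December 2013, the procedures are mostly in the past tense, and the reference list includes papers from 2015 and 2016. This affects which remedy applies. What remains is the gap: a subjective primary outcome requested by investigators, with no stated safeguard at the point of collection.

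**Conclusion.** The point holds as a gap in protection, not as proof of bias. The stated blinding does not reach the people who ask for the primary rating, so courtesy or interviewer expectation could shift ratings differentially between arms, most plausibly towards the video.

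The documents give no size. Under the stated assumptions (SD 1.0 to 1.5, 45 analysed per arm, two-sided 0.05, no true effect), a 0.25-point shift yields about 12% to 22% false-positive results and a 0.5-point shift about 35% to 65%. Modest shifts would therefore be enough to undermine the nominal 5% error rate. The safeguard is cheap enough to be worth adding without a firmer estimate.

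**What to change.** Amend the Study Procedure section so that, in both groups, every VAS-A after randomisation, including the one on arrival in the pre-operative room, is:

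- completed by the patient in private, on a form carrying only the study number;
- given with one identical written instruction that does not mention the film;
- sealed by the patient, collected unopened by staff already on the unit, and opened only at data entry.

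The cost is envelopes and a short procedural text. The patient already marks the scale, so no extra assessor is needed; I assume that unit staff are at hand, which the plan does not state for the moment of rating. The small downside is that an unclear or missing mark cannot be queried on the spot.

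This reduces courtesy and interviewer bias. It does not remove the expectation of patients who know whether they saw a film, and the plan should state that as a limitation.

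If the ratings were already collected in the stated 2013 period, the procedure cannot be changed. The report should then state who elicited the VAS-A and whether they knew the arm, and should limit the conclusion on the primary outcome accordingly.

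### The time point of the repeat vital signs is contradictory: the procedure text, read literally, puts the reading after the regional block, while other sections point to before it

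*Combined protocol and SAP*

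**What the plan says.** The Outcome row of the synopsis lists as a secondary outcome "any variance in vital parameters that are usually affected by anxiety", naming blood pressure, respiratory rate and heart rate. Measurements and Procedures has these taken at admission, 2-3 hours before the operation.

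For the repeat reading, Study Procedure/Flowchart with Timelines says: "Non-invasive arterial blood pressure, cardiac and respiratory frequency were recorded once again on arrival in the OR", and the sentence goes on to say that they were "monitored continuously throughout the anaesthetic and surgical procedure". The next paragraph says "IVRA was performed by an anaesthesiologist and a nurse in the induction room outside the OR using a standardized procedure". It describes intravenous lines and then: "after tourniquet inflation, a total volume of 40 ml of chloroprocaine 0.5% was injected intravenously in the operated limb". After that: "The patient was then transferred to the OR and 10 minutes after local anaesthetic injection, the surgeon tested loss of sensitivity with a pinprick test".

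Statistical Analysis incl. Power Analysis names three steps for analysing vital signs and VAS-A: arrival in the hospital, before leaving for the pre-operative room, and arrival in that room. The OR is not among them.

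The video description, under Study Product/Intervention, says the film covers the events "which occurs between the arrival of patients in the operating room and the performance of intra-venous regional anaesthesia". It ends with the patient being brought to the operating room once the block has been shown.

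**The concern.** The vital signs are there to support the VAS-A with a physiological measure of anxiety. The rationale says that, when the procedure is not life-threatening, much of preoperative anxiety concerns the anaesthetic, and the video prepares patients for that anaesthetic. Whether the repeat reading falls before or after the block therefore decides what the outcome measures.

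Before the block, it reflects anticipation. After it, it also carries the response to needles, tourniquet and local anaesthetic, at a time when the event the patient was prepared for is largely over. A null result could then mean either no effect or a reading taken too late. A change from admission within an arm would mix the effect of the block with everything else that happened in between, and the statistical section does plan a comparison across steps.

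If the sections disagree, the person recording the data and the analyst may each pick a different moment, and different patients may be measured at different moments.

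**Working it through.** **Order of events, section by section**

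| Section | What it implies for the repeat vital signs |
|---|---|
| Procedure/Flowchart, sentence on vital signs | Discrete reading on OR arrival. Monitoring also runs through the anaesthetic, so it must begin before or during the block |
| Procedure/Flowchart, next paragraph | Lines, tourniquet and injection in the induction room, then transfer to the OR: OR arrival is after the block |
| Statistical Analysis | Last analysed step is arrival in the pre-operative room: before the block, if that room is the induction room |
| Video description, opening and middle | OR arrival and the checks on entering come before the block |
| Video description, ending | Patient is brought to the OR after the block |

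Nowhere are pre-operative room, induction room and OR related to each other. The counts differ too: Measurements and Procedures and the flowchart text give two discrete vital-sign readings (admission and OR arrival), while the statistical section analyses three steps. No discrete vital-sign reading is scheduled for its middle step.

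**Timing on the literal reading**

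- The pinprick test comes 10 minutes after injection and after transfer, so OR arrival falls within about 10 minutes of the injection.
- The repeat VAS-A is at least 30 minutes before transfer to the OR. The injection therefore comes at least 30 − 10 = 20 minutes after the VAS-A.
- The VAS-A and the vital signs are then at least 30 minutes apart, with the injection inside that interval rather than added to it.

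**Size**

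The documents give no SD, expected difference or block response for any vital sign, so the loss cannot be computed. The only design figure, 45 per group at 90% power, is for anxiety. It cannot be reproduced, because no SD, control rate or drop-out rate is given: with a halved mean, n per group is 22, 45 or 85 for an assumed SD of 0.5, 0.73 or 1.0 times the control mean. The two illustrations below rest on assumptions (two-sided 5%, normal approximation, all 45 per group evaluable).

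*Dilution only.* The standardised difference detectable with 90% power is (1.960 + 1.282) × √(2/45) = 3.242 × 0.2108 = 0.683. If a fraction f of that effect remains at the later reading, power = Φ(3.242f − 1.960).

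| f | 3.242f − 1.960 | Power |
|---|---|---|
| 1 | 1.282 | 90% |
| 0.75 | 0.471 | 68% |
| 0.50 | −0.339 | 37% |
| 0.25 | −1.150 | 13% |

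*Dilution and noise, heart rate.* Assume SD 12 bpm, a true pre-block difference of 5 bpm, and an independent block response with SD 8 bpm.

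- Before the block: SE = 12 × √(2/45) = 2.53; 5/2.53 = 1.98; power about 50%.
- After the block: SD = √(144 + 64) = 14.42; SE = 3.04.
- Whole difference remaining: 5/3.04 = 1.64; power about 38%.
- Half remaining: 2.5/3.04 = 0.82; power about 13%.

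Even with ideal timing, power in this example is only about 50%, so a null would be weak evidence in any case.

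**The case against.** The best reply is that the protocol probably means a reading before the block. The vital-sign sentence runs from arrival to anaesthetic to surgery, in that order. The statistical section ends at arrival in the pre-operative room. The video description opens with OR arrival ahead of the block. On this view OR is used loosely for the operating suite, and the intended reading is close to the one proposed below. That is plausible, and it rules out saying that the reading is certainly post-block. It does not settle the time point: the flowchart text states the opposite order in plain words, and the video description ends in agreement with it.

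A second reply also stands. A reader might infer that vital signs on OR arrival cannot show any effect of the video. The documents do not support that. The arms differ only in the video, and the block is standardised, so the between-group difference remains an unbiased comparison of video with no video at that moment. The secondary outcome is not worded as strictly preoperative, and the stated aim speaks of perioperative anxiety. What is lost is closeness to preoperative anxiety and, probably, precision.

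Third, the primary outcome does not depend on these readings. The VAS-A precedes the injection on either reading: by at least about 20 minutes if the block comes before OR transfer, and by more than 30 if it comes after. Its timing is nonetheless anchored to the same undefined term.

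**Conclusion.** The concern holds as an inconsistency in the definition of a secondary outcome. The time point of the repeat vital signs is contradictory across three sections and cannot be resolved from the text.

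If the flowchart text is followed literally, the comparison is still randomised and unbiased for that moment. It then describes a peri-block state, with probable dilution and added noise, and within-arm change from admission is confounded by the block. The size of the loss is unknown. The power figures above show direction under assumed inputs and are not estimates for this trial.

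Severity is moderate: the point should be corrected, but the primary VAS-A comparison does not depend on it. The conclusion assumes that the room names carry their ordinary meaning wherever the text does not relate them.

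**What to change.** 1. Reconcile the video description, the statistical section and the flowchart text on the order of OR arrival and IVRA, and state how the pre-operative room, the induction room and the OR relate.
2. Define the vital-sign outcome, in both arms, as the reading on arrival in the induction or pre-operative room, before cannulation and tourniquet inflation. Compare the arms with adjustment for the admission reading, for example by ANCOVA.
3. Label any reading taken after IVRA as such, and report it descriptively.
4. Make the analysed steps match the scheduled readings: either schedule vital signs at the middle step or drop that step for vital signs.

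The cost is one changed time point and demotion of the OR-arrival reading. No new equipment is implied, since monitoring through the anaesthetic is already described. The study schedule is April to December 2013 and the procedures are in the past tense, so the data may already be collected. In that case the fix depends on a pre-cannulation value having been recorded: the text says values were monitored, not that they were stored. If none exists and the reading was taken after the block, label the result as after IVRA and do not interpret it as preoperative anxiety.
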